5.4.2.1 Measurable Lesions

Measurable lesions must be accurately measured in at least two perpendicular dimensions. For subjects staged with PET-CT (DLBCL, PTCL, PMBL and MGZL), focal uptake in nodal and extranodal sites that is in keeping with lymphoma, according to the distribution and/or CT characteristics, is considered involvement with lymphoma, including spleen, liver, bone, thyroid, and so on. For subjects staged with CT, up to six of the largest target nodes, nodal masses, or other lymphomatous lesions that are measurable in two diameters (longest diameter [LDi] and shortest diameter) should be identified from different body regions representative of the patient's overall disease burden and include mediastinal and retroperitoneal disease, if involved. A measurable node must have a LDi greater than 15 mm. Measurable extranodal disease (eg, hepatic nodules) may be included in the six representative, measured lesions. For extranodal measurable lesion the LDi must be greater than 10 mm. All other lesions (including nodal, extranodal, and assessable disease) should be followed as non measurable disease (eg, cutaneous, GI, bone, spleen, liver, kidneys, pleural or pericardial effusions, ascites). In subjects in whom a discordant histology or malignant transformation is suspected, a PET-CT may identify the optimal site to biopsy for confirmation.

For subjects with CTCL measurable, skin lesions are defined as papules, plaques and patches covering $\geq 10\%$ of the skin surface (T2). Lymph nodes are qualified as abnormal if > 15 mm in diameter.

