Partial Lymph nodes and extralymphatic sites	Partial metabolic response Score 4 or 5† with reduced uptake compared with baseline and residual mass(es) of any size At interim, these findings suggest responding disease At end of treatment, these findings indicate residual disease	Partial remission (all of the following) ≥ 50% decrease in SPD of up to 6 target measurable nodes and extranodal sites When a lesion is too small to measure on CT, assign 5 mm × 5 mm as the default value When no longer visible, 0 × 0 mm For a node > 5 mm × 5 mm, but smaller than normal, use actual measurement for calculation
Nonmeasured lesions	Not applicable	Absent/normal, regressed, but no increase
Organ enlargement	Not applicable	Spleen must have regressed by > 50% in length beyond normal
New lesions	None	None
Bone marrow	Residual uptake higher than uptake in normal marrow but reduced compared with baseline (diffuse uptake compatible with reactive changes from chemotherapy allowed). If there are persistent focal changes in the marrow in the context of a nodal response, consideration should be given to further evaluation with MRI or biopsy or an interval scan	Not applicable
No response or stable disease Target nodes/nodal masses, extranodal lesions	No metabolic response Score 4 or 5 with no significant change in FDG uptake from baseline at interim or end of treatment	Stable disease < 50% decrease from baseline in SPD of up to 6 dominant, measurable nodes and extranodal sites; no criteria for progressive disease are met
Nonmeasured lesions	Not applicable	No increase consistent with progression
Organ enlargement	Not applicable	No increase consistent with progression
New lesions	None	None
Bone marrow	No change from baseline	Not applicable

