*A score of 3 in many patients indicates a good prognosis with standard treatment, especially if at the time of an interim scan. However, in trials involving PET where de-escalation is investigated, it may be preferable to consider a score of 3 as inadequate response (to avoid undertreatment). Measured dominant lesions: Up to six of the largest dominant nodes, nodal masses, and extranodal lesions selected to be clearly measurable in two diameters. Nodes should preferably be from disparate regions of the body and should include, where applicable, mediastinal and retroperitoneal areas. Non-nodal lesions include those in solid organs (eg, liver, spleen, kidneys, lungs), GI involvement, cutaneous lesions, or those noted on palpation. Nonmeasured lesions: Any disease not selected as measured, dominant disease and truly assessable disease should be considered not measured. These sites include any nodes, nodal masses, and extranodal sites not selected as dominant or measurable or that do not meet the requirements for measurability but are still considered abnormal, as well as truly assessable disease, which is any site of suspected disease that would be difficult to follow quantitatively with measurement, including pleural effusions, ascites, bone lesions, leptomeningeal disease, abdominal masses, and other lesions that cannot be confirmed and followed by imaging. In Waldeyer's ring or in extranodal sites (eg, GI tract, liver, bone marrow), FDG uptake may be greater than in the mediastinum with complete metabolic response, but should be no higher than surrounding normal physiologic uptake (eg, with marrow activation as a result of chemotherapy or myeloid growth factors).

†PET 5PS: 1, no uptake above background; 2, uptake ≤ mediastinum; 3, uptake > mediastinum but ≤ liver; 4, uptake moderately > liver; 5, uptake markedly higher than liver and/or new lesions; X, new areas of uptake unlikely to be related to lymphoma.

*The recommendations from Lugano Classification is to use a 5 point scale to assess the metabolic response in PET-CT based response.

Response Evaluation in DLBCL, PTCL, PMBL & MGZL:

CR (Complete Remission)

The designation of CR requires all of the following be met:

- 1) Complete disappearance of all detectable clinical evidence of disease.
 - a) PET-CT-based response: A score of ≤ 3 is considered to represent complete metabolic response.

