 - b) CT based response: Target node/nodal masses must regress to ≤ 1.5 cm in LDi, with no extralymphatic sites of disease.

Organ involvement: Absence of organomegaly (Table 3).

- 2) Bone marrow: No evidence of FDG-avid disease in marrow. If there was evidence of involvement of bone marrow with lymphoma at screening/baseline and a biopsy was performed (PTCL), a bone marrow biopsy will be required to confirm CR.
- 3) The presence of residual symptoms in the absence of detectable disease by imaging does not preclude the designation of CR.

PR (Partial Remission)

The designation of PR requires all of the following:

- 1) PET-CT based response: Score of 4 or 5, provided reduced uptake compared with base line and absence of structural progression development on CT Scan.

- 2) CT based response: $\geq 50\%$ regression in SPD of upto 6 measurable nodal and extranodal lesions (Table 3) .
- 3) Splenic and hepatic nodules must regress by $\geq 50\%$ in length beyond normal.

Bone marrow : reduced uptake compared with baseline. If there is evidence of nodal response but persistent focal changes in the marrow consider further evaluation (Table 3).

SD (Stable Disease)

SD is defined as the following:

- 1) PET-CT based response: no metabolic response, score of 4 or 5 with no significant changes from baseline.
- 2) CT based response: $< 50\%$ decrease from baseline, absence of new lesions (Table 3).
- 3) Bone marrow: no change from baseline.

PD: Relapsed Disease (after CR)/Progressive Disease (after PR, SD)

- 1) PET-CT based response: Score of 4 or 5 with increase in intensity from baseline or interim scan/ or any new FDG avid focus consistent with malignant lymphoma (Table 3).
- 2) CT based response: New node, new or recurrent splenomegaly, progression of existing lesions (Table 3).

IR (INDETERMINATE RESPONSE)

A patient will be considered to have Indeterminate Response (IR) in one or more of the 3 following circumstances

- 1) Increase in overall tumor burden (as assessed by SPD) of $\geq 50\%$ of up to 6 measurable lesions in the first 12 weeks of therapy, without clinical deterioration (IR(1))
- 2) Appearance of new lesions; or growth of one or more existing lesion(s) of $\geq 50\%$ at any time point during treatment occurring in the context of lack of overall progression ($<50\%$ increase) of overall tumor burden, as measured by SPD of up to 6 lesions at any time during the treatment (IR(2))

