*A biopsy of normal appearing skin is unnecessary to assign a complete response. However, a skin biopsy should be performed of a representative area of the skin if there is any question of residual disease (persistent erythema or pigmentary change) where otherwise a complete response would exist. If histologic features are suspicious or suggestive of mycosis fungoides/Sézary syndrome (see histologic criteria for early mycosis fungoides⁷), the response should be considered a partial response only.

†Whichever criterion occurs first.

Table 5: Response in Lymph Nodes*

Response	Definition
CR	All lymph nodes are now ≤ 1.5 cm in greatest transverse (long axis) diameter by method used to assess lymph nodes at baseline or biopsy negative for lymphoma; in addition, lymph nodes that were N ₃ classification and ≤ 1.5 cm in their long axis and > 1 cm in their short axis at baseline, must now be ≤ 1 cm in their short axis or biopsy negative for lymphoma
PR	Cumulative reduction $\geq 50\%$ of the SPD of each abnormal lymph node at baseline and no new lymph node > 1.5 cm in the diameter of the long axis or > 1.0 cm in the diameter of the short axis if the long axis is 1-1.5 cm diameter
SD	Fails to attain the criteria for CR, PR, and PD
PD†	$\geq 50\%$ increase in SPD from baseline of lymph nodes or Any new node > 1.5 cm in the long axis or > 1 cm in the short axis if 1-1.5 cm in the long axis that is proven to be N ₃ histologically or Loss of response: $> 50\%$ increase from nadir in SPD of lymph nodes in those with PR
Relapse	Any new lymph node > 1.5 cm in the long axis in those with CR proven to be N ₃ histologically

Abbreviations: CR, complete response; PR, partial response; SPD, sum of the maximum linear dimension (major axis) \times longest perpendicular dimension (minor axis); SD, stable disease; PD, progressive disease.
*Peripheral and central lymph nodes.
†Whichever criterion occurs first.

Table 6: Response in Viscera

Response	Definition
CR	Liver or spleen or any organ considered involved at baseline should not be enlarged on physical exam and should be considered normal by imaging; no nodules should be present on imaging of liver or spleen; any post treatment mass must be determined by biopsy to be negative for lymphoma
PR	≥ 50% regression in any splenic or liver nodules, or in measurable disease (SPD) in any organs abnormal at baseline; no increase in size of liver or spleen and no new sites of involvement
SD	Fails to attain the criteria for CR, PR, or PD

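### Appendix 2 holds two conflicting partial-response rules for spleen and liver disease, and nothing says which one decides the primary ORR

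*Protocol*

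**What the plan says.** Protocol 8.3.1 defines the primary ORR as subjects with a best response of CR or PR over treated subjects, and refers the investigator to Appendix 2 for every histology except CTCL. SAP 4.1 cites only the Lugano 2014 classification.

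Appendix 2 states PR in two places.

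- **Table 1, CT column.** Organ enlargement: "Spleen must have regressed by > 50% in length beyond normal". Lesions: at least a "50% decrease in SPD of up to 6 target measurable nodes and extranodal sites". The table's footnote counts solid-organ disease among measurable lesions: "Non-nodal lesions include those in solid organs (eg, liver, spleen, kidneys, lungs" and others. Protocol 5.4.2.1 agrees: "Measurable extranodal disease (eg, hepatic nodules) may be included in the six representative, measured lesions".
- **Table 1, PET-CT column.** PR is a score of 4 or 5 "with reduced uptake compared with baseline and residual mass(es) of any size". The organ-enlargement row is marked not applicable.
- **PR text after the table.** It opens with "The designation of PR requires all of the following". Item 1 is labelled PET-CT and item 2 is labelled CT. Item 3 has no modality label: "Splenic and hepatic nodules must regress by" at least 50% in length beyond normal. No item requires an enlarged spleen to regress.

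**The concern.** The two statements differ in four respects: the object tested (the spleen, or nodules in spleen and liver), the measure for nodules (SPD, or length), the threshold (more than 50%, or at least 50%) and the modality (CT only, or unrestricted). Length beyond normal makes sense for an organ that has a normal length. A nodule has none.

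Nothing in the documents settles the conflict. Neither document ranks the table above the text. Neighbouring lines of the PR text point to a Table 3, but the Protocol's Table 3 is the mSWAT skin-scoring table in Appendix 4.

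Response is investigator-assessed. Two investigators who each follow Appendix 2 could therefore classify the same subject differently, and PR counts directly in the primary ORR of B1, B2, B4 and B5. CTCL (B3) uses the Global Response Score and is not affected.

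**Working it through.** **1. The plan's own figures.** Inputs from Protocol 8.1 and SAP 7.5.1: one-sided alpha 10%, two-sided 80% Clopper-Pearson interval, and the cohort sizes, null rates and target rates. The lower limit L for x responders solves P(X ≥ x | n, L) = 0.10. A cohort succeeds if L exceeds the null rate p0. With r the smallest successful count, power = P(X ≥ r | n, p1).

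| Cohort | n | p0 / p1 | r | Power computed (stated) | L at r | L at r − 1 | One subject |
|---|---|---|---|---|---|---|---|
| B1 | 40 | 40% / 60% | 21 | 87.0% (87%) | 41.2% | 38.8% | 1/40 = 2.5 points |
| B2 | 30 | 40% / 60% | 16 | 82.5% (82%) | 40.1% | 37.0% | 1/30 = 3.3 points |
| B4 | 30 | 30% / 50% | 13 | 81.9% (81%) | 30.8% | 27.7% | 1/30 = 3.3 points |
| B5 | 10 | 10% / 30% | 3 | 61.7% (61%) | 11.6% | 5.5% | 1/10 = 10 points |

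The stated power and intervals reproduce. In each cohort, one responder fewer than r moves the lower limit below the null rate.

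**2. Enlarged spleen, CT-followed, no nodules, SPD down by at least 50%.** Table 1's progression example has a 15 cm spleen progressing only above 16 cm. The 1 cm rise is 50% of the prior excess, so the excess is 2 cm and the implied normal length is 15 − 2 = 13 cm. For a spleen going from 17 to 16.5 cm:

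- excess before: 17 − 13 = 4.0 cm
- excess after: 16.5 − 13 = 3.5 cm
- fall: 0.5 / 4.0 = 12.5%, where more than 50% is required

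Table 1: not PR. PR text: PR, because no item asks for spleen regression.

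**3. Sole measured lesion, a liver nodule, CT-followed, 40×40 to 25×25 mm.**

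- product: 1,600 to 625 mm², a fall of 975 / 1,600 = 61%
- length: 40 to 25 mm, a fall of 15 / 40 = 37.5%

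Table 1, CT column: the SPD criterion for PR is met. Item 3, if read as halving of length: not PR. For a lesion shrinking equally in both axes, a 50% fall in product is a length fall of 1 − √0.5 = 29.3%, and a 50% fall in length is a product fall of 1 − 0.5² = 75%.

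**4. PET-followed subject with reduced uptake and a nodule 25% shorter.** Table 1, PET-CT column: PR, since residual masses of any size are allowed. Item 3 read literally: not PR, because it carries no CT label and every item is required.

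So the PR text can both add and remove responders relative to Table 1.

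**The case against.** The strongest reply is that this is one badly worded line beside a table that remains in force. The endpoint text names Lugano 2014, which Table 1 sets out, and most subjects in these histologies are to be followed by FDG PET-CT, where Table 1 has no organ-size test. Much of this stands. If investigators simply use Table 1, item 3 does no harm, and if the PET and CT routes are taken as alternatives with item 3 belonging to CT, the conflict is confined to CT-followed subjects. But item 3 is worded as a requirement and not limited to CT, and no text tells the investigator to disregard it.

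Several stronger readings are tempting, and the documents do not support them.

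- **That the text replaces Table 1, or that the spleen goes unassessed.** Table 1 still stands. The text also requires no organomegaly for CR, no structural progression for PR, and treats new or recurrent splenomegaly as progression. Only its PR spleen-regression rule is missing.
- **That any nodule shrinking 29% to 50% in length passes Table 1.** That holds only for a sole or representative lesion shrinking equally in both axes. Add an assumed node going from 60×50 to 55×48 mm to the nodule above: SPD goes from 4,600 to 3,265 mm², a fall of 29%, and Table 1 is not met.
- **That item 3 is definitely a stricter test.** Halving of length is one reading; the line may equally be a garbled spleen rule.
- **That PR makes up most of ORR in all four cohorts.** The documents do not say so. Protocol 1.1.3 reports 8 CR and 6 PR in PTCL-NOS and 5 CR and 2 PR in AITL with brentuximab vedotin.
- **That the cohorts are underpowered.** The share of subjects with spleen or liver disease is not given. If an assumed 2% to 10% of responders were lost, B1 power would be 83% to 64%. If instead 2% to 10% of non-responders were gained at the null rate, its one-sided error would be 9.9% to 25.2%, against 7.4%. These scenarios are not estimates, and the direction is unknown.

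Appendix 4, Table 6 asks for at least 50% "regression in any splenic or liver nodules, or in measurable disease (SPD) in any organs abnormal at baseline", with no reference to normal length. It governs CTCL only and cannot settle the matter.

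**Conclusion.** Wrong as written. Appendix 2 contains two PR rules for spleen and liver disease that disagree on object, measure, threshold and modality, with no order of precedence, and PR feeds the primary endpoint directly.

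The effect is conditional. It needs a subject with an enlarged spleen or with splenic or hepatic nodules, close to the PR boundary. For PET-followed subjects it arises only through a literal reading of item 3. One such subject moves ORR by 2.5 points in B1, 3.3 in B2 and B4, and 10 in B5, and reverses the conclusion if the cohort sits at 21/40, 16/30, 13/30 or 3/10. These figures use the planned Cohort B sizes; SAP 7.1 pools Cohort A subjects by histology, which makes each step slightly smaller. The total effect on ORR cannot be calculated from the documents. The planned sample size, power and intervals are not in error.

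The spleen case assumes the 13 cm normal length implied by Table 1. The nodule case assumes a sole measured lesion and item 3 read as halving of length.

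**What to change.** Reconcile item 3 of the PR text with Table 1, the Lugano table on which the endpoint relies. Suggested content: *For CT-based response, an enlarged spleen must lose more than 50% of its excess over normal length. Splenic and hepatic nodules are assessed within the SPD if measured, and otherwise as nonmeasured lesions. For PET-CT-based response, the organ-size item does not apply.*

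This takes a sentence or two in Appendix 2 and should be in place before responses are derived for the primary analysis. It needs no new data, procedure or sample-size change. Responses already recorded for subjects with spleen or liver disease should be checked against the reconciled rule.

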8.3.2 Secondary Endpoint(s)

The secondary endpoints are DOR, CR rate, duration of CR, PFS and OS.

DOR will be calculated from the date of initial documentation of a response (CR, or PR) to the date of first documented evidence of progressive disease (or relapse for subjects who experience CR during the study) or death. Subjects who are progression-free and alive or have unknown status will be censored at the last tumor assessment. For subjects who received subsequent therapy prior to documented progression, duration of response will be censored on the last tumor assessment date prior to subsequent therapy. Allogeneic SCT and ASCT will be considered as subsequent therapy.

The CR rate is defined as the number of subjects with a BOR of CR divided by the number of treated subjects. The duration of CR will only be evaluated in subjects with BOR of CR and is defined as the time from first documentation of CR to the date of initial documented progression or death due to any cause, whichever occurs first. Censoring will be applied as per DOR definition.

PFS is defined as the time from the date of first dose of study drug until the date of first documented evidence of progressive disease (or relapse for subjects who experience CR during the study) or death, whichever comes first. Subjects who are progression-free and alive or have unknown status will be censored at the last tumor assessment. For subjects who received subsequent therapy prior to documented progression, it will be censored on the last tumor assessment date prior to subsequent therapy.

OS is defined as the time from the date of first dose of study drug until the date of death (any reason). If the subject is alive or the vital status is unknown, the subject will be censored at the date the subject was last known to be alive.

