Progressive disease Individual target nodes/nodal masses Extranodal lesions	Progressive metabolic disease Score 4 or 5 with an increase in intensity of uptake from baseline and/or New FDG-avid foci consistent with lymphoma at interim or end-of-treatment assessment	Progressive disease requires at least 1 of the following PPD progression: An individual node/lesion must be abnormal with: LDi > 1.5 cm and Increase by ≥ 50% from PPD nadir and An increase in LDi or SDi from nadir 0.5 cm for lesions ≤ 2 cm 1.0 cm for lesions > 2 cm In the setting of splenomegaly, the splenic length must increase by > 50% of the extent of its prior increase beyond baseline (eg, a 15-cm spleen must increase to > 16 cm). If no prior splenomegaly, must increase by at least 2 cm from baseline New or recurrent splenomegaly
Nonmeasured lesions	None	New or clear progression of preexisting nonmeasured lesions

(continued on following page)

Response and Site	PET-CT-Based Response	CT-Based Response
New lesions	New FDG-avid foci consistent with lymphoma rather than another etiology (eg, infection, inflammation). If uncertain regarding etiology of new lesions, biopsy or interval scan may be considered	Regrowth of previously resolved lesions A new node > 1.5 cm in any axis A new extranodal site > 1.0 cm in any axis; if < 1.0 cm in any axis, its presence must be unequivocal and must be attributable to lymphoma Assessable disease of any size unequivocally attributable to lymphoma
Bone marrow	New or recurrent FDG-avid foci	New or recurrent involvement

Abbreviations: 5PS, 5-point scale; CT, computed tomography; FDG, fluorodeoxyglucose; IHC, immunohistochemistry; LDi, longest transverse diameter of a lesion; MRI, magnetic resonance imaging; PET, positron emission tomography; PPD, cross product of the LDi and perpendicular diameter; SDi, shortest axis perpendicular to the LDi; SPD, sum of the product of the perpendicular diameters for multiple lesions.

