- 3) Increase in FDG uptake of one or more lesion(s) without a concomitant increase in lesion size or number (IR(3))

It is possible that, at a single time point a subject could fulfill criteria for both IR(1 or 2) AND IR(3): for example, there could be a new FDG-avid lesion in the absence of overall progression (IR(2)), and, at the same time, increase in FDG uptake of a separate lesion (IR(3)). In such cases, the designation of IR(1 or 2) should take priority (eg, IR(2))

Follow-up of IR

- 1) In patients categorized as having any of the above types of IR, it is mandatory to obtain a repeat imaging after an additional 12 weeks (or earlier if clinically indicated). At that time, response should be re-evaluated and the patient should be considered to have true PD if the SPD of target lesion has increased further, with the considerations below:
- 2) In the case of IR(1), the comparison should be between the first IR(1) and the current SPD, with an increase of >10% constituting PD. In addition there should be an increase of > 5 mm (in either dimension) of at least one lesion for lesions < 2 cm, and 10 mm for lesions > 2 cm, to be consistent with the Lugano classification (3)(Table 2). The 10% threshold is empiric but designed to account for variability in measurement (37), especially when taken along with the minimum increase. If the target SPD increase is < 10%, the response would still be categorized as IR(1), and the patient could continue treatment until a subsequent scan shows either true PD (> 10% increase from first IR(1) time point and an increase of > 5mm in either dimension of at least one lesion) or response (>50% decrease from baseline). In this situation, it is reasonable to repeat imaging in 4-8 weeks of the original IR(1) timepoint to ensure absence of significant further increase.
- 3) In the case of IR(2), the new or growing lesion(s) (unless biopsy proven to be benign) should be added to the target lesion(s), up to a total of no more than 6 total lesions. If the SPD of the newly defined set of target lesions has increased > 50% from the nadir value which may precede the IR time point. The patients is considered to have PD.
- 4) In the case of IR(3), since inflammatory responses may result in an increase in the standardized uptake value of a lesion, the patient will not be considered to have PD unless there is evidence of PD by an increase in lesion size or the development of new lesions, as noted above

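### Appendix 2 gives three answers (PR, PD or indeterminate) for a PET rebound that stays below baseline, so the DOR and PFS event date is not fixed for such subjects

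*Protocol*

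**What the plan says.** Protocol 5.4 makes FDG PET-CT the main basis of response in DLBCL, PTCL, PMBL and MGZL. Appendix 2 then gives the rules for these cohorts in three places.

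- Table 1, PET column. Progression: "Score 4 or 5 with an increase in intensity of uptake from baseline and/or New FDG-avid foci consistent with lymphoma". Partial response is a score of 4 or 5 "with reduced uptake compared with baseline and residual mass(es) of any size".
- Response text after the table. Progression: "Score of 4 or 5 with increase in intensity from baseline or interim scan/ or any new FDG avid focus" consistent with lymphoma. Partial response: "Score of 4 or 5, provided reduced uptake compared with base line and absence of structural progression development on CT Scan". The text refers the reader to Table 3, which in this protocol is the mSWAT skin table in Appendix 4.
- Indeterminate response (LYRIC). A rise in FDG uptake with no increase in lesion size or number is IR(3). It is not PD unless lesions grow or new ones appear. If true PD follows with no response in between, the PD is dated back to the IR designation.

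Protocol 8.3.2 runs DOR from first response "to the date of first documented evidence of progressive disease (or relapse for subjects who experience CR during the study) or death", and PFS ends at the same event. Protocol 8.3.1 and SAP 4.1 close the BOR window at progression. Protocol 5.4 assesses objective response by Lugano 2014 together with LYRIC. SAP 4.2 bases the secondary endpoints on Lugano 2014 (Global Response Score for CTCL) and names no PET reference scan.

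**The concern.** The two PET progression rules use different reference scans, and the LYRIC rule gives a third outcome. Interim scan is not defined, although treatment continues to progression with repeated scans, so almost any earlier on-study scan could qualify. The text also overlaps with itself: uptake above an earlier scan but below baseline meets both its PD wording and its PET wording for PR.

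Response is assessed by investigators at many sites, and each could follow a different sentence in good faith. The date at stake ends DOR, duration of CR and PFS. The cohorts are single-arm, so no concurrent comparison would absorb a difference in how that date is set.

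**Working it through.** **Inputs.** Scans at weeks 6 and 12, then four at 9-week intervals (weeks 21, 30, 39, 48), then every 12 weeks (Protocol 5.4.1). Duration = last date − first date + 1, and 1 month = 30.4375 days (SAP 8); the same convention is applied here to PFS. Uptake values are assumed for illustration: baseline 12, then 5, 8 and 13 at weeks 6, 12 and 21. All on-study scans score 4 or 5, at the same sites, with no growth and no new focus.

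**The rules side by side.**

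| Rule in Appendix 2 | Reference scan | Week 12 (uptake 8) | Week 21 (uptake 13) |
|---|---|---|---|
| Table 1 | baseline | PR (8 < 12) | PD (13 > 12) |
| Text | baseline or interim | PD (8 > 5), though PR wording also met | event already dated |
| IR(3) | not stated | IR(3), not PD | still not PD on uptake alone |

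**Event dates.**

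- Table 1: DOR = (21 − 6) × 7 + 1 = 106 days (3.5 months); PFS = 21 × 7 + 1 = 148 days (4.9 months).
- Text: DOR = (12 − 6) × 7 + 1 = 43 days (1.4 months); PFS = 12 × 7 + 1 = 85 days (2.8 months).
- Difference: 63 days, one 9-week interval. In weeks, DOR is 6 against 15, or longer if uptake passes baseline later than week 21.
- IR(3): no event on uptake alone. If growth or a new lesion later establishes PD without an intervening response, back-dating returns the event to week 12, if the first IR designation is the one meant.

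**Landmarks.** SAP 7.5.2 may report PFS at 6 and 12 months, which are 6 × 30.4375 / 7 = 26.1 weeks and 365.25 / 7 = 52.2 weeks. A move from week 21 to 30 crosses the first; a move from week 48 to 60 crosses the second.

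**BOR.** Assume that uptake of 3 or less is a complete metabolic response and that confirmed means response at two consecutive scans. The protocol gives no repeat-scan rule for the Lugano cohorts.

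| Uptake at successive scans | SAP, unconfirmed: Table 1 / text | Protocol, confirmed: Table 1 / text |
|---|---|---|
| 5, 8, 13 | PR / PR | PR / none |
| 5, 5, 8, 13 | PR / PR | PR / PR |
| 5, 8, 2, 2 | CR / PR | CR / none |

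Under the SAP's definition ORR changes in none of the three sequences, and the CR rate changes in one.

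**Stated powers.** Exact binomial, one-sided 10%: B1 at least 21/40, 87.0% (stated 87%); B2 at least 16/30, 82.5% (82%); B3 at least 16/20, 63.0% (62%); B4 at least 13/30, 81.9% (81%); B5 at least 3/10, 61.7% (61%). All reproduce within about one point, and none depends on the PET rule.

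**Exposure.** 40 + 30 + 30 + 10 = 110 planned Cohort B subjects. This is a ceiling, because disease that is not PET-avid at baseline is followed by CT. Cohort A subjects with these subtypes, whom SAP 7.1 pools in, would add a few.

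**The case against.** The best reply is that Appendix 2 already answers the case: an isolated rise in uptake is IR(3) and not PD, and Protocol 5.4 brings LYRIC into objective response. That stands as a third reading but does not settle the matter. Protocol 8.3.3 makes indeterminate response exploratory, and SAP 4.2 cites Lugano 2014 alone. Even if that sets LYRIC aside, Table 1 and the text are both presented as Lugano and still disagree.

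Other replies narrow the point, and they stand:

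- A reader might infer that under Table 1 loss of response is seen only once uptake exceeds its pre-treatment level. The documents do not support this. New foci count in Table 1, and the CT column measures progression from nadir, so a rebound with growth can be PD on the same date under either rule.
- A reader might infer that ORR falls. A recorded responder stays a responder, because BOR is the best response before progression. SAP 4.1 does not ask for a confirmed response; only the protocol does.
- After CR the case is weaker. A returning site may be called a new focus, and the DOR and PFS definitions name relapse separately.
- Progression at unscheduled visits counts (SAP Table 4.2-1), and scans have windows of 1 to 2 weeks, so a full interval is typical of the shift but not its minimum.

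**Conclusion.** The contradiction is real and should be corrected. It concerns a defined case: a score of 4 or 5, uptake above an earlier on-study scan but below baseline, no new focus and no CT progression. Such a subject is PR under Table 1, PD under the text and IR(3) under LYRIC. The DOR and PFS event can then move by about one scheduled scan interval, illustrated by week 12 against week 21 on assumed uptake values.

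BOR changes only if a PR deepens to CR after the rebound, or if the protocol's confirmation wording governs and the rebound comes first. The primary ORR analysis as the SAP defines it, and its stated powers, are not affected for recorded responders. The documents give no frequency of such rebounds, so the effect on cohort medians cannot be estimated.

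A reader might also infer, from the nadir rule in the CT column, that PET progression should be measured from nadir. The documents do not establish that. Such a rule would conflict with IR(3), and because Appendix 2 progression feeds Protocol 4.5.5 it would in effect choose a criterion for stopping treatment.

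**What to change.** 1. Reconcile Table 1, the response text and the indeterminate-response rules in Appendix 2, so that Table 1 and the text name the same single PET reference scan. Define interim scan if the term is kept.
2. Correct the text's Table 3 cross-reference.
3. State in SAP 4.2 which PET reference scan, and which handling of IR(3) including its back-dating, set the progression date for BOR, DOR, duration of CR and PFS.
4. Check that on-study PET scores and uptake are captured as that rule requires. SAP 7.3.2 lists the 5-point scale and maximum SUV only among baseline characteristics, and neither document shows uptake values being recorded at each visit.
5. Reconcile Protocol 4.5.5 and 4.5.9, which rely on Appendix 2 progression, with the appendix. This point takes no view on which clinical rule is right.

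The cost is minor wording in the appendix and the SAP, with no new scans, plus any case report form change that step 4 shows to be needed. Reported DOR and PFS may come out somewhat shorter or longer depending on the rule chosen, so it should be fixed before the data are analysed.
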